An Ovaprene™ postcoital test (PCT) study in 21 women has been published.¹ Historically, the PCT was developed to evaluate couples with infertility, but it has been used in the initial evaluation of vaginal chemical and mechanical contraceptive barriers. In that setting, the PCT can demonstrate that, in the absence of the barrier, progressively motile sperm from the male partner can achieve access into the woman's midcycle cervical mucus, and, in the presence of the barrier, this access is reduced or eliminated. Three vaginal barrier devices, Lea's Shield, FemCap™, and the SILCS diaphragm (also known as Caya®), were evaluated by a postcoital study and then by a contraceptive effectiveness study prior to FDA approval. No progressively motile sperm were seen in midcycle mucus among all 10 users of Lea's Shield+Nonoxynol-9 (N-9) or in any of the 13 users of SILCS (Caya) diaphragm + N-9, and 6-month typical use pregnancy rates of 8.7% and 12.5% were observed in the subsequent contraceptive efficacy studies, respectively. Progressively motile sperm were seen in midcycle mucus in 1 of 7 users of FemCap+N-9 and a 6-month typical use pregnancy rate of 13.5% was observed in the contraceptive efficacy study. If PCT testing of Ovaprene™ were to show results similar to the results of these FDA-approved diaphragms, it is likely that Ovaprene™ would also show similar results in a contraceptive effectiveness study.

In the standard PCT test referenced above, the definition of a successful barrier function requires that thin cervical mucus is present during ovulation and that despite this, fewer than 5 progressively motile sperm per high power field (HPF) are seen in the cervical mucus. If the cervical mucus is thick, which may be the case if ovulation does not occur or if the test is done before or after ovulation, and there are fewer than 5 progressively motile sperm per HPF, the cycle must be repeated on the grounds that the thickness of the mucus may have prevented the appearance of sperm in it. Since Ovaprene™ is designed to release acid, which may increase cervical mucus viscosity, the interpretation of the PCT will require modification. The expected result, if Ovaprene™ is effective, will be fewer than 5 progressively motile sperm per high power field (HPF) in the cervical mucus, regardless of whether the mucus is thin or thick.

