- If sperm are found in the vagina or cervical mucus, the baseline cycle will be rescheduled for the following month and instructions on the use of condoms will be reviewed. Additional supplies will be provided as needed.
- If the cervical mucus score is <10, the participant may be asked to return in 1 or 2 days if it seems likely that the midcycle point has not yet been reached, or in the next cycle if it seems likely that the midcycle point has already passed.
- If no sperm are detected at this visit, and the cervical mucus score is ≥10, the participant will be instructed to have vaginal intercourse without a condom 2 to 3 hours prior to Visit 3 (BP2), which will be scheduled for the same or following day, within 27 hours of the mucus check visit.
- The participant will be instructed to otherwise avoid any other vaginal activitiesh until after Visit 3 (BP2).
- The participant will be instructed to ask her partner, prior to her next visit, if he has had any AEs involving the urogenital system or whether he has had any serious AEs.

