#### b) Visit OP2, the CMC visit, on the day of the "high" result or the next:

- Diary review, AEs, medications, and indications for a directed physical exam, wet mount, and other tests will be managed as described for Visit 2 (BP1).
- The participant will be asked whether she used condoms until Day 10 and then refrained from intercourse and the use of intravaginal products, and whether her male partner refrained from ejaculation since Day 10. If instructions were not followed, she will be reinstructed. If she used a spermicide or spermicidal lubricated condom since day 10, Visit OP2 will be rescheduled in the next cycle. Otherwise, the visit may continue at the investigator's discretion.
- The participant will undergo a pelvic exam:
  - o Signs of irritation of the external genitalia, cervix, and vagina, as observed with the naked eye, will be noted.

<sup>s "Other vaginal activity" includes insertion of vaginal medications/products other than the study product (prescription or over-the-counter), as well as insertion of sex toys, fingers, or anything else into the vagina. Tampons may be used during all days of menses in the Baseline PCT and Caya PCT cycles, but only during the first three days of menses in Ovaprene cycles.

Version: 06.00 (FINAL) Date: June 13, 2019

- o The position of the device relative to the cervix will be noted.
- o Cervical mucus will be examined for pH, ferrous gluconate, midcycle characteristics, and the presence of sperm (see **Appendix 2**).
- o Vaginal sample(s) will be collected for pH, ferrous gluconate, and the presence of sperm.
- o It is expected that the cervical mucus could be thick and should be without sperm at the CMC. If sperm are found in the vagina or cervical mucus, this cycle will be rescheduled and instructions on condom use and abstinence will be reviewed.
- o If no sperm are detected in the vagina or cervical mucus, the participant will be instructed to have intercourse without a condom but with the device in place, 2 to 3 hours prior to the next visit, which will be scheduled for the same or following day, within 27 hours of the mucus check visit.
- o The participant will be instructed to otherwise avoid any other vaginal activitiest until after Visit OP3.

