# c) Visit OP3, the PCT visit, 2-3 hours after intercourse and within 27 hours of the CMC:

The participant will return to the clinic 2-3 hours after coitus ends and within 27 hours of the mucus check visit.

- Diary review, AEs, medications, and indications for a directed physical exam, wet mount, and other tests will be managed as described for Visit 2 (BP1)
- An acceptability questionnaire will be administered.
- The participant will undergo a pelvic exam:
  - o Signs of irritation of the external genitalia, cervix, and vagina, as observed with the naked eye, will be noted.
  - o The position of the device relative to the cervix will be noted.
  - o Cervical mucus will be examined for pH, ferrous gluconate, midcycle characteristics, and the presence of sperm (see **Appendix 2**).
  - o Vaginal sample(s) will be collected for pH, ferrous gluconate, and the presence of sperm.
  - o At sites other than EVMS, vaginal samples will be collected for antibacterial activity and soluble markers.
  - Results of the test PCT will be interpreted as shown in Appendix 3. A successful test PCT will show mucus containing an average of <5 progressively motile sperm per HPF.
- At the EVMS site only:
  - o At 0.5, 1, 2, 4, and 6 hours after the PCT: u
    - Vaginal sample(s) will be collected for pH and ferrous gluconate.
  - o At 6 hours after the PCT, if possible:

<sup>t "Other vaginal activity" includes insertion of vaginal medications/products other than the study product (prescription or over-the-counter), as well as insertion of sex toys, fingers, or anything else into the vagina. Tampons may be used during all days of menses in the Baseline PCT and Caya PCT cycles, but only during the first three days of menses in Ovaprene cycles.

<sup>u Samples will be collected at as many of these timepoints as possible.

Version: 06.00 (FINAL) Date: June 13, 2019

- Vaginal sample(s) for antibacterial activity and soluble markers will be collected.
- The participant will be instructed to refrain from intercourse and other vaginal activity until after Visit OP4, 24 hours after Visit OP3.

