# APPENDIX 2. ACTIONS AT THE PCT VISIT IN BASELINE AND TEST CYCLES (ADAPTED FROM SCHWARTZ ET AL, 2008)

		2008 /							
Vaginal pool - any sperm present (including	Mucus – adequate (thin)	Endocervix No sperm	Some sperm but an average of <5	An average of ≥5	Action at Baseline Cycle	Action at Test Cycle			
fragments) *			progressively motile/HPF**	progressively motile/HPF					
Yes	Yes	✓			Similar results in test				
Yes	Yes		✓		cycle would make it appear that the product	Barrier successful			
No	Yes		✓		was successful. Do not continue participant.	Continue to next cycle.			
Insufficient material	Yes		✓						
Yes	Yes			✓		Barrier failed.			
Yes	No			✓		If Caya cycle, do not continue participant if			
No	Yes			✓	Good PCT. Continue to	the result was clearly due to participant misuse of the product. Otherwise, continue to			
No	No			✓	next cycle				
Insufficient material	Yes			✓		next cycle. If Ovaprene ™ cycle, continue to next cycle.			
Insufficient material	No			✓		continue to next cycle.			
Yes	No	✓				If Caya cycle, repeat cycle.			
Yes	No		✓		Poor mucus may be responsible for scarcity or	If Ovaprene ™ cycle, continue to next cycle.			
No	No		✓		lack of sperm in cervix. Repeat cycle.	Considered successful for Ovaprene™ due to its			
Insufficient material	No		✓			potential mucus- thickening properties.			
No	Yes	✓							
No	No	✓			Ejaculation may not have taken place. Repeat cycle.	Ejaculation may not have taken place.			
Insufficient material	Yes	✓			taken place, kepeat cycle.	Repeat cycle.			
insufficient material	No	✓	:						

\* Absence of sperm in vagina means either that ejaculation did not take place or the vaginal environment is unusually hostile to sperm, possibly due to presence of spermicide in Caya cycle.

\*\* Confirms that ejaculation took place, but presumed to be insufficient for conception

Version: 06.00 (FINAL) Date: June 13, 2019

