- c) Levels of ferrous gluconate in CVF before sex that are associated with fewer than 5 progressively motile sperm per HPF in the cervical mucus after sex (i.e. success), during ovulation. Summary statistics of sample size, mean, median, standard deviation, and IQR will be presented by visit.
- d) Levels of ferrous gluconate in CVF at multiple time points in the safety cycle in the absence of coitus. This will allow the estimation of how long after insertion it takes to reach the target concentration levels associated with success and whether target levels are still present up to 29 days after insertion. Summary statistics of sample size, mean, median, standard deviation, and IQR will be presented by visit and assessment timepoint.
- e) Levels of ferrous gluconate in CVF before and at multiple time points after sex at ovulation with the device in place. This will allow determination of whether they are different from before sex and, if so, how much time is needed to return to pre-sex levels at all visits in Ovaprene® PCT cycles in both vaginal and cervical fluid. Summary statistics of sample size, mean, median, standard deviation, and IQR will be presented by visit and assessment time-point.
- f) Vaginal pH (from Vaginal Sample CRF) and cervical pH (from Cervical Mucus CRF) before and after sex in the absence and presence of the device. Six-number summary for the observed values and difference between pre-sex and after sex will be presented by visit. For the study site (EVMS only) with multiple timepoints at a visit, the summary will be done at each timepoint. The average of pH values within each visit over the multiple timepoints will be calculated for each subject, and then be summarized. The goal of these assessments during the Ovaprene® safety cycle is to look at the effect of study device in the absence of sex.
- g) Residual amount of ferrous gluconate in Ovaprene® devices that have been worn over a cycle of use. Six-number summary statistics will be presented by visit and by duration of time the device was worn (1-7 days, 8-14 days, 15-21 days, 22-28 days and >28 days).
- h) Cervical mucus score. Summary statistics mean, median, standard deviation, and IQR will be presented by visit. The number and percent of subjects with cervical mucus score ≥ 10 in each Ovaprene cycle will also be presented. For the summary of cervical mucus score ≥ 10, cervical mucus data will only be used from the cycle that occurs after the highest OPK result for that cycle.

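### Ovaprene PCT success carries no mucus-adequacy condition, and no planned table shows how much of the primary proportion comes from thick-mucus cycles

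*Protocol*

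**What the plan says.** The Introduction explains why a standard PCT with thick mucus and few sperm is not accepted: "the cycle must be repeated on the grounds that the thickness of the mucus may have prevented the appearance of sperm in it". It also says when thick mucus arises: "which may be the case if ovulation does not occur or if the test is done before or after ovulation". It then modifies the reading for Ovaprene, because acid released by the device may thicken mucus. Fewer than 5 PMS/HPF is the expected result "regardless of whether the mucus is thin or thick".

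The visit procedures follow this. At the baseline mucus check (Section 9.2.1) the couple proceeds to intercourse and the PCT on the condition "If no sperm are detected at this visit, and the cervical mucus score is ≥10", and Section 9.3.2 sets the same requirement for Caya. At the Ovaprene mucus check (Section 9.5.1 b) the only condition is absence of sperm, and the text adds: "It is expected that the cervical mucus could be thick and should be without sperm at the CMC". At the Ovaprene PCT visit (Section 9.5.1 c), "A successful test PCT will show mucus containing an average of <5 progressively motile sperm per" HPF. That section refers to Appendix 3 for interpretation, but the PCT table is in Appendix 2.

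| Step | Baseline | Caya | Ovaprene |
|---|---|---|---|
| Trigger for mucus check | OPK 'high' | OPK 'high' | OPK 'high' |
| Mucus score ≥10 before the PCT | Required | Required | Not required |
| Thick mucus, <5 PMS/HPF, evidence of sperm | Repeat | Repeat | Success |
| Thick mucus, ≥5 PMS/HPF | Good PCT | Failed | Failed |
| No sperm in mucus; none, or insufficient material, in vaginal pool | Repeat | Repeat | Repeat |

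For the thick-mucus success, Appendix 2 gives the reason "Considered successful for Ovaprene™ due to its" potential to thicken mucus.

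SAP 3.6 c) and f) count cycles with an average below 5. A cycle is dropped only when sperm are lacking in both vaginal pool and mucus. Under h), "The number and percent of subjects with cervical mucus score ≥ 10 in each Ovaprene cycle will also be presented", using mucus data from after the highest OPK result. Six subgroup analyses are listed, none by mucus score.

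**The concern.** Section 5.1 gives the purpose as preventing sperm from entering midcycle mucus. A low count in thick mucus has two possible explanations: the device worked, perhaps by thickening the mucus, or the mucus was not midcycle mucus and would have held few sperm anyway. The protocol names the second explanation, removes the usual safeguard against it for Ovaprene only, and plans no analysis that shows its extent.

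The OPK trigger does not settle the matter. Baseline and Caya cycles use the same trigger, and the protocol still adds the mucus score there, with instructions to return in 1 or 2 days or in the next cycle when the score is below 10. Exclusion criterion 22 allows for two failed mucus attempts with no device in place. So the protocol itself accepts that a 'high' reading need not coincide with adequate mucus.

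What is at stake is how the main result is read. The Introduction argues from PCT results like those of approved barriers to similar contraceptive effectiveness, and it describes the standard PCT as needing thin mucus. The Caya cycle, meant to give confidence in the Ovaprene results, is also held to that stricter standard.

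**Working it through.** The plan gives no power, significance level or expected proportion on this point, so there is no figure to reproduce. The check is a bound on the possible bias.

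**Inputs**
- m: share of analysed Ovaprene PCT cycles that are mistimed or anovulatory with thick mucus. Not in the documents; assumed 10% to 40%.
- p: true success proportion in adequate, well-timed cycles. Not in the documents; assumed 50% to 95%.
- s: share of the mistimed thick-mucus cycles that read below 5 PMS/HPF. Not in the documents.

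**Formula**

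Apparent proportion = m·s + (1 − m)·p, so the error is m(s − p).

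If thick mucus lets through no more sperm than thin mucus, s is at least p and the error cannot be negative. It is largest at s = 1, where it equals m(1 − p). Appendix 2 has rows for thick mucus with 5 or more PMS/HPF, so the protocol does not treat s as 1, and the figures below are ceilings.

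**Apparent proportion at the ceiling, m + (1 − m)p**

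| True p | m = 10% | m = 20% | m = 30% | m = 40% |
|---|---|---|---|---|
| 50% | 55% | 60% | 65% | 70% |
| 70% | 73% | 76% | 79% | 82% |
| 80% | 82% | 84% | 86% | 88% |
| 90% | 91% | 92% | 93% | 94% |
| 95% | 95.5% | 96% | 96.5% | 97% |

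Away from the ceiling the error shrinks. With m = 20%, p = 80% and s = 90% it is 0.20 × (0.90 − 0.80) = 2 points, against 4 at the ceiling.

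**Illustration with 25 women, m = 20%, p = 80%**
- Thick-mucus cycles: 0.20 × 25 = 5, all counted as successes at the ceiling.
- Adequate cycles: 20, with 0.80 × 20 = 16 successes.
- As planned: (5 + 16)/25 = 84.0%, exact 95% CI 63.9% to 95.5%.
- Adequate mucus only: 16/20 = 80.0%, exact 95% CI 56.3% to 94.3%.

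The plan sets no success threshold. As a further illustration, the chance of at least 23 successes in 25 at p = 80% is 0.098 with m = 0, 0.213 with m = 20% and 0.300 with m = 30%, again at the ceiling.

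**The case against.** The case on the other side is substantial. Timing is controlled: the Ovaprene mucus check is scheduled on the day of an OPK 'high' result or the next, the PCT follows within 27 hours, participants report regular 24-35 day cycles, and women with two failed mucus attempts at baseline are excluded. Five or more PMS/HPF is a failure whatever the mucus. Cycles with no evidence of sperm are repeated, and the SAP excludes them. The rule is disclosed and reasoned; if thickening is part of how the device works, those cycles are true successes. The endpoint is descriptive, and Section 14.2.2 rules out a statistical comparison with Caya. Mucus score is summarised by visit and cycle and tied to OPK timing, and the by-subject mucus and OPK listings would let a reader cross-check about 25 women.

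Most of this stands. It shows that one safeguard is missing, not that timing is uncontrolled, and it is good reason to leave the primary rule alone. It does not supply the missing analysis. The OPK restriction in SAP 3.6 h) governs the mucus summary, not the PCT proportion. No passage requires an OPK peak or confirms ovulation before the Ovaprene PCT. A cross-check that a reader could do by hand from listings is not a pre-specified result.

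**Conclusion.** The point holds in a limited form. Ovaprene cycles are judged without the mucus-adequacy condition applied at baseline and with Caya. The primary proportion could therefore be too high, and the planned tables would not show by how much. The direction rests on the assumption that thick mucus does not help sperm through. The size is unknown and at most m(1 − p): up to 20 points if p is 50% and m is 40%, and no more than 2 points over the same range of m if p is 95%. The ceiling is higher for a mediocre device, which is the case that a feasibility study most needs to recognise.

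A reader might infer that mistimed or anovulatory cycles pass automatically and that the primary proportion is inflated. The documents support neither statement. Such a cycle must still follow an OPK 'high' result, show evidence of sperm and fall below 5 PMS/HPF, and nothing in the documents says how often mistiming happens. No type I error or power statement is affected, because the plan makes none.

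**What to change.** Keep the primary success rule. In SAP 3.6 c) and f), pre-specify the following:

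1. A cross-tabulation of PCT result (<5 against ≥5 PMS/HPF) by mucus score (≥10 against <10), once with the score at OP2 and once with the score at OP3.
2. Beside the primary figure, the proportion below 5 PMS/HPF with exact 95% CI in cycles scoring at least 10, described as conservative if the device itself thickens mucus. For f), which pools up to two cycles per woman, note that an exact binomial interval treats them as independent.
3. A descriptive split by whether the OPK diary recorded a 'peak' around the PCT, with cycles lacking OPK entries shown separately. The protocol does not say when testing may stop, so a missing peak is not proof of no ovulation. Restricting instead to OP2 visits on the day of or after 'high' would add little: that is already the scheduling rule, and it would not identify anovulatory cycles.

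The cost is some SAP wording and a small number of tables from mucus scores and OPK entries already collected. The restricted proportion rests on fewer cycles. When all n cycles succeed, the exact lower bound is 0.025^(1/n): 80.5% for 17/17 against 86.3% for 25/25. Neither split fully separates device thickening from mistiming, because mucus score is measured with the device in place. They would show how far the headline figure depends on thick-mucus cycles.

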# APPENDIX 3. CORRECT FIT OF OVAPRENE™ AND CAYA

The criteria below must be met in two situations:

- For the clinician to conclude that the device fits a participant, assessed at Visit 1 for Caya and BP3 for Ovaprene™
- For the clinician to conclude that the participant has correctly positioned the device, assessed at Visit 1, BP3, and in cycles in which the Ovaprene™ or Caya device is used

#### Fit criteria:

- 1. Location: the device should cover the cervical os and not protrude outside the introitus
- 2. Security: the device should not be easily dislodged by the clinician's finger
- 3. Comfort: the participant should not report discomfort or pain

Version: 06.00 (FINAL) Date: June 13, 2019

#### LIST OF ABBREVIATIONS

#### Abbreviation Explanation

AE Adverse Event
BMI Body Mass Index
BV Bacterial Vaginosis
CRF Case Report Form
CSR Clinical Study Report
CVF Cervicovaginal Fluid

EVMS Eastern Virginia Medical School FDA Food and Drug Administration

FG Ferrous Gluconate

HIV Human Immunodeficiency Virus

HPF High Power Field IQR Interquartile Range

MedDRA Medical Dictionary for Regulatory Activities

OPK Ovulation Predictor Kit

OVP Ovaprene®
PCT Postcoital Test

PMA Premarket Approval – Food and Drug Administration

PMS Progressively Motile Sperm
SAE Serious Adverse Event
SAP Statistical Analysis Plan
SD Standard Deviation
UTI Urinary Tract Infection
WHO World Health Organization

#### 1.0 INTRODUCTION

This statistical analysis plan (SAP) was developed after review of the DR-OPV-001 study protocol V06.00 (13 June 2019) and case report forms (CRFs) V7.00 (13 May 2019), but before any analysis of the data had begun. Detailed information is given to aid in the production of the statistical outputs and the statistical section of the final clinical study report (CSR). This document gives a summary of the protocol and describes the populations that will be analyzed. All subject characteristics, efficacy, safety, acceptability, and device fit parameters that will be evaluated, along with the specific statistical methods, are described. If the actual analysis is deviated, but not that significantly different, from this document, no amendment to SAP will be done, and the changes will be described in the final CSR.

#### 2.0 PROTOCOL SUMMARY

#### 2.1 Background

Ovaprene® (OVP) is a single use, hormone-free contraceptive device for female contraception. It consists of a flexible ring combined with a knitted polymer barrier insert. The ring component is comprised of a liquid silicone rubber matrix that is combined with a proprietary mixture of ferrous gluconate (FG), ascorbic acid (Vitamin C), glycine, and polyglycolide microparticles. Historically, the PCT was developed to evaluate couples with infertility, but it has been used in the initial evaluation of vaginal chemical and mechanical contraceptive barriers. If PCT testing of Ovaprene® were to show results similar to the results from Food and Drug Administration (FDA)-approved diaphragms, such as Lea's Shield, FemCap®, and the SILCS diaphragm (also known as Caya®), it is likely that Ovaprene® would also show similar results in a contraceptive effectiveness study. An Ovaprene® postcoital test (PCT) study in 20 women was published in 2009.¹ It demonstrated proof of concept in terms of demonstrating no progressively motile sperm (PMS) seen in cervical mucus with the device in place. This new study is designed to provide more evidence of changes in the PCT results with and without the OVP in place, as well as safety and acceptability.

